If participants' self-assessment indicates that they are eligible, they will proceed to the second stage of screening, otherwise their sign-up will end and they will not be able to use the app further, nor be included in the trial. Once a participant has provided informed consent, registered, and confirmed they meet the eligibility criteria, their onboarding phase ends and their baseline phase starts, which is elaborated in the next section.

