2.2.4 Randomisation

Randomisation will be conducted at the household level. This approach has two advantages over individual-level randomisation: (i) avoids the risk of contamination within the same household (but opens up the possibility of additive effects of multiple household members being in treatment together); (ii) reduces the risk that we alienate and / or confuse users in the control group whenever they cohabit with someone assigned to a treatment arm.

Users will enter randomisation only if/when they have completed the baseline phase. This implies that the day of randomisation is different across users even within the same households: it always happens at the end of their baseline phase (if successful), but the exact calendar day depends on when they have downloaded the app, when they have completed the onboarding, and how long it took them to complete the baseline phase (see Figure 1 for an example from a user's perspective).

The randomisation algorithm developed by HUL would then:

1. Check if another user from the same household has already been randomised

¹⁴ We consider the attrition too high if the number of users not providing their data is 10% smaller than expected at the start of the 1 month mark (see Table 6 for the expected attrition at different trial stages).

¹⁵ Results for the 5m mark will still be reported; however, we will rely on results from the 3m mark to provide an assessment of the impact of offering financial incentives.

based on their full addresses (including postcode).

- 2. If YES, the algorithm assigns this user to the same trial arm
- 3. If NO, the algorithm generates a random number from 1-100 (inclusive) for the user.
- 4. Based on the rule described in Figure 2, users are assigned to one of the 4 trial arms. Note that the control arm will be larger than the other arms. This is because at the analysis stage (5m mark), we aim at having 3 users in the control group for each user in the treatment arms. However, we expect attrition to differ across control and treatment groups, as shown in Table 6 in Section 2.4.2.4.. Based on these attrition estimates, at randomisation 12% of users will be assigned to the high incentive arm, 12% to the medium incentive arm, 15% to the low incentive arm, 61% to the control arm.

BIT's in-house IT expert will quality assure the code of the randomisation algorithm developed by HUL before the trial launch.

Figure 1. Onboarding and baseline phase from a user's point of view¹⁶.

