2.4.2.3 Minimum required sample size at the participant recruitment stage

The minimum required sample size at the analysis stage is not necessarily the sample we need at the participant recruitment stage. An important consideration is the proportion of participants who are expected to drop out of the study post-randomisation and for whom we will not have any outcome data (i.e. *the attrition rate*). To have a well-powered sample for analysis requires setting recruitment targets that are substantially higher to account for this attrition during the trial. In their acquisition plan, HUL estimated the attrition rates by treatment conditions (see Table 6 for details).

Trial arm				Estim	ates				
	N at the beginning of the baseline period	N at the end of the baseline period (at randomisation)	Attrition rate at 1m mark	N needed at 1m mark	Attrition rate at 3m mark	N needed at 3m mark	Attrition rate at 5m mark	N needed at 5m mark	Attrition from the beginning of the baseline period to the 5m mark
High incentive	~3,100	~1,900	18%	1,550	44%	1,050	62%	700	77%
Medium incentive	~3,200	~1,950	18%	1,600	45%	1,100	63%	700	78%
Low incentive	~3,800	~2,250	21%	1,800	50%	1,150	69%	700	81%
Control group	~15,700	~9,400	26%	6,950	60%	3,800	78%	2,100	87%
Total	~25,800	~15,500	-	~11,900	-	~7,100	-	4,200	-
Note: Attrition rate between baseline and randomisation: 40% for all groups									

Table 6. Estimated sample size required at various trial stages given the corresponding estimated attrition rate

This is consistent with systematic reviews of digital health interventions showing attrition rates of up to 80% in some RCTs (*average* attrition is 40-50%), and a common indication of differential attrition between trial arms.⁴⁷

Based on the estimated attrition rate, HUL and DHSC agreed on a target sample size of **25,800** (3,100 in the high incentive group; 3,200 in the medium incentive group; 3,800 in the low incentive group; 15,700 in the control group) **at the beginning of the baseline phase.**

⁴⁷ Meyerowitz-Katz et al. (2020); Howarth et al. (2018); Beleigoli et al. (2019).

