4.2.2. Reach, acquisition, and usage analysis

The reach, acquisition, and usage analysis will focus on (i) quantifying the number of consenting users and breaking down this sample by relevant subgroups, (ii) quantifying the amount of engagement with the app during the duration of the pilot and exploring how engagement levels vary by study arm, (iii) identifying study-level and personal-level predictors of engagement with the app.

Table 16 describes the metrics that will be analysed. The feasibility of the planned analyses rely on HUL's ability to share the in-app metrics described in Table 16 with BIT, which has been confirmed by HUL.

Metric	Data source	Number of timepoints		Which subgroups
Number of consenting users recruited from launch until recruitment finishes (in N)	In-app data	1 (total timespan)	5	Total and by study arm
% of randomised adults that are very active users (defined as app installed and opened at least once over the course of 7 days) per week from randomisation to week 24 (in %)	In-app data	22 (weekly)	5	Total and by study arm
% of randomised adults that are churn-out users (defined as app not opened since more than 30 days from randomisation to week 24) (in %)	In-app data	22 (weekly)	5	Total and by study arm

Table 16	Motrico	undorlying	the reach	occuricition	and upper a	nalvoia
	weincs	unuenvinu	life reach	. accuuisillon.	and usage a	11012515
				,		

Number of consenting users from launch until recruitment finishes (in N), by subgroup	In-app data	1 (total timespan)		Total and by study arm. Each respectively by deprivation status (2 groups), ethnicity (5 groups), sex (3 groups), age (2 groups), baseline F&V intake (2 groups), baseline MVPA (2 groups).
---------------------------------------------------------------------------------------------	-------------	-----------------------	--	------------------------------------------------------------------------------------------------------------------------------------------------------------------------------------------------------------------------

The above metrics will be analysed descriptively using summary statistics.

Additionally, we will conduct a regression analysis to identify the factors predicting the proportion of intervention period during which consenting participants are categorised as being very active (defined as app installed and opened at least once over the course of the last 7 days). The factors explored in the regression will include:

- age,
- sex,

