4.2.3. Engagement with the intervention and mechanisms of action

As indicated in the ToC, beyond the initial engagement with the intervention (e.g. providing in-app consent), continued engagement with the app is critical to driving behavioural change in PA and diet activity.

This includes successful onboarding during the baseline stage, selecting and completing challenges, logging behaviours, verifying behaviours, and redeeming incentive rewards.

To explore these themes, the quantitative IPE will analyse the metrics summarised in Table 17. All data will be collected via the app or by reward providers and will be obtained from HUL. The analyses outlined in this section will also rely on HUL sharing the metrics described in Table 17 with BIT.

Table 17. Metrics underlying the 'engagement with the intervention and mechanisms of action' analysis

	Data	Number of	Number of	
Metric	source	timepoints	groups	Which groups
% of consenting participants completing their profile before randomisation (in %)	In-app data	1 (total timespan)	1	Total sample
% of consenting participants connecting the wearable device before randomisation (in %)	In-app data	1 (total timespan)	1	Total sample
% of consenting participants that are active during the "new user journey" (defined as app opened at least once every 7 days over the 30 days after randomisation) (in %)	In-app data	1 (total timespan)	5	Total and by study arm
Average daily number of hours the wearable device is worn from consent to week 24 (in N)	In-app data	1 (total timespan)	5	Total and by study arm
Average daily number of hours the wearable device is worn per week from consent to week 24, by week (in N)	In-app data	22 (weekly)	5	Total and by study arm
Average number of PA challenges selected per week from randomisation to week 24 (in N)	In-app data	1 (total timespan)	5	Total and by study arm
Average number of PA challenges successfully completed per week from randomisation to week 24 (in N)	In-app data	1 (total timespan)	5	Total and by study arm
Average number of PA challenges successfully completed per week by difficulty from randomisation to week 24 (in N)	In-app data	1 (total timespan)	5	Total and by study arm for three difficulty levels
Weekly number of PA challenges successfully completed from randomisation to week 24, by week (in N)	In-app data	22 (weekly)	5	Total and by study arm for three metrics

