Average cumulative value of redeemed rewards from randomisation to week 24 (in £) by subgroup	Reward partners	1 (total timespan)	80	Total and by study arm. Each respectively by deprivation status (2 groups), ethnicity (5 groups), sex (3 groups), age (2 groups), baseline F&V intake (2 groups), baseline MVPA (2 groups).

Summary descriptive statistics (e.g., averages, proportions) will be calculated using data on all metrics in Table 17 to provide an overview of in-app engagement for the entire participant sample (i.e. all participants who sign up to the app and provide in-app consent, regardless of subsequent data completeness), and split by trial arm.

Additionally, for key metrics related to continued app usage, summary statistics will also be visualised on a weekly basis across the intervention period to provide further insights about how users' behaviour changes over time.

As specified in the table above, to uncover potential differences in engagement between different population segments, **subgroup analyses will be conducted for key metrics, namely:**

- Average number of PA challenges completed from randomisation to week 24
- Average number of diet challenges completed from randomisation to week 24
- Average cumulative number of points earned (**both verified and unverified**) from randomisation to week 24
- Average cumulative value of redeemed rewards from randomisation to week 24

The characteristics and cut offs used for these subgroup analyses will be the same as those employed as part of the impact evaluation.

We will also conduct a regression analysis to identify the factors predicting the cumulative number of points earned from randomisation to week 24, which is used to estimate users' success rate at selecting and completing diet and physical activity challenges. The factors explored in the regression will include age, sex, baseline obesity status (BMI \ge 25), ethnicity, deprivation status, disability status, education, brand of wearable, treatment arm (control, low incentives, medium incentives, high incentives), baseline MVPA, and baseline fruit and vegetable intake. The cut offs for each predictor will be defined following the same criteria used in the impact evaluation (unless specified above).

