4.2.4. Analysis of 'gaming' and data errors

The final section of the quantitative IPE will involve a descriptive analysis of 'gaming' and data errors. Table 18 summarises the metrics that will be used to conduct this analysis. These metrics will be operationalised and collected from HUL and our analyses rely on HUL sharing these metrics.

Metric	Data source	Number of timepoints	Number of groups	Which groups
% of consenting participants with unreasonable body measurements (e.g. BMI over 100 kg/m2) at any timepoint from randomisation to week 24 (in %)	In-app survey	1 (total timespan)	5	Total and by study arm
% of non-validated points earned by study arm from randomisation to week 24 (in %)	In-app data	1 (total timespan)	5	Total and by study arm
% of non-validated points earned by study arm, per month from randomisation to week 24 (in %)	In-app data	5 (monthly)	5	Total and by study arm
Subgroup analysis on the % of non-validated points earned by study arm from randomisation to week 24	In-app data	1 (total timespan)	80	Total and by study arm. Each respectively by deprivation status, ethnicity, sex, age, baseline F&V intake, baseline MVPA.

Table 18. Metrics underlying the	'potential gaming and data errors' analysis.
rable re: meaned and mying are	potoritial garning and data orroro analysis.

Summary statistics will be calculated using data on the above metrics for the entire participant sample and by study arm. Additionally we will conduct subgroup analyses on the % of non-validated points earned by study arm from randomisation to week 24 to understand if potential gaming and data error varies by deprivation status, ethnicity, sex, age, baseline F&V intake, baseline MVPA. This section of the quantitative IPE will help to quantify the extent of 'gaming' and data errors in the intervention.

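### Two process measures counted from randomisation use all consenting users as denominator, so their totals would be at most about 0.60 of the value among randomised users

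*Protocol*

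**What the plan says.** The order of events is clear. Section 2.2.2.3 states: "Once a participant has provided informed consent, registered, and confirmed they meet the eligibility criteria, their onboarding phase ends and their baseline phase starts". Section 2.2.4 adds: "Users will enter randomisation only if/when they have completed the baseline phase". A user therefore consents first and has an arm only after completing baseline. User D in the Figure 1 example starts baseline, does not supply the data and is never randomised.

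The quantitative process evaluation nevertheless uses consenting users for windows that open at randomisation:

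- Section 4.2.3, text after Table 17: the sample for all Table 17 metrics is "all participants who sign up to the app and provide in-app consent, regardless of subsequent data completeness", then split by trial arm.
- Table 17, third row, whose window is the first 30 days from randomisation and which is reported in total and by arm: the percentage "of consenting participants that are active during the 'new user journey' (defined as app opened at least once every 7 days".
- Table 18, first row: the percentage "of consenting participants with unreasonable body measurements", from randomisation to week 24, in total and by arm.
- Section 4.2.2, regression (4): the outcome is "the proportion of intervention period during which consenting participants are categorised as being very active", with study arm as a predictor.

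Table 16 takes a different line. Its weekly very-active and churn-out rows are percentages of randomised adults.

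**The concern.** A percentage describing behaviour after randomisation has a clear meaning only among people who were randomised. Someone lost before that point cannot be active in the 30 days after it, and cannot record a body measurement in a window that starts with it. Counting such people in the denominator mixes loss before randomisation with engagement or data quality after it.

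Section 4.2.3 is meant to answer how far the scheme engages participants overall, and the total column is the direct answer. For the new user journey, the total would make engagement look weaker than it was. For unreasonable body measurements the error is in the reassuring direction: the total would understate possible gaming or data error. In both rows the total would not agree with the arm figures printed beside it.

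**Working it through.** **Inputs (Table 6 and the text of section 2.4.2.3)**

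- Start of baseline: "3,100 in the high incentive group; 3,200 in the medium incentive group; 3,800 in the low incentive group; 15,700 in the control group". Sum: 3,100 + 3,200 + 3,800 + 15,700 = 25,800.
- Randomised: 1,900 + 1,950 + 2,250 + 9,400 = 15,500.
- Stated loss: "Attrition rate between baseline and randomisation: 40% for all groups".

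**Reproducing the plan's figure**

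1 − 15,500/25,800 = 0.399. By arm the loss is 38.7% (high), 39.1% (medium), 40.8% (low) and 40.1% (control). In the other direction, 25,800 × 0.60 = 15,480. The stated 40% is reproduced. It leaves 25,800 − 15,500 = 10,300 expected baseline starters without an arm.

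**Effect on a percentage**

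Let p be the percentage among randomised users. Unrandomised users add nothing to the numerator, so:

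total on the consenting denominator = p × N randomised / N consenting.

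Consent precedes baseline, so N consenting is at least the number starting baseline, and the factor is at most 15,500/25,800 = 0.601. With assumed values of p:

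| p among randomised (assumed) | total as planned, at most |
|---|---|
| 90% | 54% |
| 70% | 42% |
| 50% | 30% |

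The factor falls further if some users consent but never start baseline. The protocol gives no number for them. As assumptions, 28,000 consenters would give 15,500/28,000 = 0.55, and 31,500 (the registration cap in section 2.2.3) would give 15,500/31,500 = 0.49.

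**Consistency of total and arms**

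The arm columns can hold only randomised users, so their weighted average is p. The total column is at most 0.601 × p. If every arm stood at 70%, the total would read 42%, below all four arms.

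**Other measures**

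- Cumulative counts and totals are unchanged, because unrandomised users contribute nothing.
- Averages from randomisation (challenges selected or completed per week, for example) shrink by the same factor only if unrandomised users are scored as zero. If they are left out as undefined, the average is right, but the analysed set is not the one section 4.2.3 names. The text does not settle which applies.
- The remaining Table 18 rows are percentages of points, not of people, and are not diluted.
- The first Table 16 row splits the number of consenting users by arm. That can be done only for those later randomised, so on the planning figures the arm counts would sum to about 15,500 against a total of about 25,800.

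**The case against.** The strongest reply is that little is affected. Table 16 already reports weekly activity and churn among randomised adults, in total and by arm, so a reader has a sound engagement measure whatever the new-user-journey row shows. The phrase about data completeness can be read as a guard against restricting the summaries to outcome completers. Consenting users are also the proper denominator for profile completion and device connection. All of this stands, and it limits the damage. It does not change the denominator written into the two percentage rows.

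A reader might infer more than the protocol supports:

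- *That the by-arm figures are undefined or diluted.* An arm exists only after randomisation, so the arm columns contain randomised users only and can be computed.
- *That unrandomised users would form a fifth group in the regressions.* Treatment is its own term with four named categories. The rule that makes missing values a separate category is written for the covariates X. Unrandomised users also have no outcome, since both outcomes cover time after randomisation. They would drop out, and the arm coefficients are not biased.
- *That regression (5) is stated on consenting users.* This is only implied, by the general sample definition in 4.2.3. It is explicit only for regression (4).
- *That engagement as a whole is understated.* The understatement is certain for two percentage rows, in the total column, and only one of them measures engagement.

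Deferral to a later analysis plan is a weak defence. Section 4.2 describes this as the final version of the quantitative process evaluation, and the populations are stated rather than left open.

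**Conclusion.** The point holds in a limited form. For two rows, one in Table 17 and one in Table 18, the stated denominator gives a total of at most about 0.60 of the percentage among randomised users. That total is not a weighted average of the arm figures, and the denominator conflicts with the one used in Table 16. For the other measures counted from randomisation, and for regression (4), the stated population is wrong but need not bias the result.

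The size rests on the delivery partner's planning estimate of 40% loss between baseline and randomisation; the actual loss may differ. Section 2.2.2.1 attaches the 25,800 to users starting onboarding, while sections 2.4.1 and 2.4.2.3 attach it to the start of baseline. The 0.60 ceiling follows from the 40% rate itself and does not depend on which is meant. The defect exists at any non-zero loss before randomisation.

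The consequence is confined to the descriptive process evaluation. The primary impact analysis and the comparison of arms are not affected.

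**What to change.** In sections 4.2.2 to 4.2.4, define two populations and assign every measure to one:

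- *Consenting users*: only the pre-randomisation reach and funnel measures (number consenting, profile completed, device connected), reported in total.
- *Randomised users*: every measure whose window starts at randomisation or that is split by arm. This includes the new-user-journey percentage, the body-measurement percentage, and the challenge, points and reward summaries. It also includes regressions (4) and (5).

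Amend the sample definition after Table 17 to match, keeping its intent that nobody is excluded for incomplete data after randomisation. Where counts by arm are wanted in Table 16, report the number randomised.

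The cost is a wording change. Table 16 already has the right phrasing to extend, and no new data are needed, because the arm splits already require randomisation status.
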